5.7.2 RAD51 Foci Formation Assay (Functional HR assay)

5.7.2.1 Specimen Receipt and Processing at the ETCTN Biorepository

For this correlative, 10 unstained, uncharged 4 micron slides from each biopsy (pre-treatment, on-treatment and pre-progression, if applicable) will be created, labeled appropriately, and sent to the laboratory of [name] of Dana Farber Cancer Institute. The slides will be packed at ambient conditions and sent by overnight courier to:

[name].; Re: NCI 10250 Harvard Institutes of Medicine HIM324/331 Center for DNA Damage and Repair [name]

Prior to shipment, an e-mail will be sent to [name] ([contact]) to inform the laboratory of the shipment.

5.7.2.2 Site Performing Correlative Study

The RAD51 foci formation assay will be performed in pre-treatment, on-treatment and optional 'pre-progression' biopsies at the Brigham and Women's Hospital Pathology Core under the direction of [name] of Dana Farber Cancer Institute. The RAD51 stain will be performed on the VENTANA platform and Geminin stains are performed on the BOND platform using standardized protocols. Antibodies to RAD51, geminin and H2AX are obtained from commercial sources that meet GMP standards. Paraffin sections of a mini-tissue microarray containing irradiated and unirradiated breast cancer cell lines MDA-MB436 (BRCA1 mutant), MDA-MB-468 (BRCA1/2-WT) and the ovarian cancer cell line KURAMOCHI (BRCA2 mutant) will be used as controls.

5.8 Exploratory/Ancillary Correlative Studies

Specimens from this study will be received, accessioned, paraffin embedded and stored per ETCTN Biorepository guidelines. Once the study is completed and all material has been received, slides will be made and distributed in batch to the laboratories performing the MGMT and SLFN11 correlative studies. The prioritization of tissue for the study is shown in Section 5.6.

5.8.1 MGMT Expression

5.8.1.1 Specimen Receipt and Processing at the ETCTN Biorepository

For this correlative, 10 unstained, uncharged slides from the pre-treatment and pre-progression biopsy (if applicable) will be created, labeled appropriately, and sent to the laboratory of [name] of the National Cancer Institute for MGMT expression analysis. The slides will be packed at ambient conditions and sent by overnight courier to:

Translational Pharmacodynamics Research Group Developmental Therapeutics Branch, CCR, NCI, NIH [name][name] 20892 [contact]

Prior to shipment, an e-mail will be sent to: [name] ([contact]) and [name] ([contact]) to inform the laboratory of the shipment.

5.8.1.2 Site Performing Correlative Study

MGMT protein (and possibly RNA expression) will be evaluated using established methodology in pre-treatment and optional 'pre-progression' biopsies in the laboratory of [name], Developmental Therapeutics Branch, NCI.

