1.3 Exploratory Objectives

- 1.3.1 To evaluate what proportion of uterine LMS tumors exhibit HR deficiency as measured by Schlafen family member number 11(SLFN11) protein expression at baseline. To evaluate the feasibility of this assay in human tissue, and to preliminarily evaluate for any association between presence of HR deficiency as measured by this assay and increased clinical benefit from the study treatment.
- 1.3.2 To evaluate MGMT protein expression in uterine LMS tumors, and to preliminarily evaluate for any association between MGMT expression and increased clinical benefit from the study treatment.
- 1.3.3 To perform an optional third tissue biopsy in patients who initially benefit from study treatment but later show early evidence of disease progression to evaluate for changes in the status of the RAD51 foci, MGMT, and SLFN11 assays at that time.

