MGMT promoter methylation has been evaluated as a biomarker for response to TMZ in glioblastoma, where TMZ is standard of care in the adjuvant and metastatic treatment settings. The effects of MGMT promoter methylation on clinical benefit from TMZ were evaluated retrospectively using tumor specimens from a phase 2 randomized study of adjuvant radiotherapy versus adjuvant radiotherapy + TMZ following definitive resection of glioblastoma (Hegi et al., 2005). Using methylation-specific PCR, 45% of cases were considered to have MGMT promoter methylation which was associated with prolonged survival from TMZ treatment. In a separate study, MGMT promoter methylation was associated with higher objective response rates to TMZ in advanced, recurrent glioblastoma (Paz et al., 2004). Retrospective clinical studies have suggested MGMT promoter methylation predicts for increased clinical benefit from TMZ in pancreatic neuroendocrine tumors, melanoma, colorectal cancer and other tumor types (Campana et al., 2018; Sartore-Bianchi et al., 2017; Tuominen et al., 2015). In addition, reexpression of the MGMT enzyme by several means, including epigenetic modification, has been described as a mechanism of resistance to TMZ monotherapy, and therefore reevaluating the status of MGMT protein expression in the on-treatment and preprogression biopsies is also of interest (Zhang et al., 2012).

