5. BIOMARKER, CORRELATIVE, AND SPECIAL STUDIES

5.1 Summary Table for Specimen Collection

Time Point	Specimen	Send Specimens To:			
PRE-TREATMENT (after informed consent and within 14 days of Cycle 1 Day 1)					
	• 4-8 formalin fixed cores ¹	ETCTN Biorepository			
	• 10 mL blood in EDTA tube				
ON-TREATMENT	(C2 D3-5, 2-6 hours post AM olaparib and tem	ozolomide treatment)			
	• 4-6 formalin fixed cores ¹	ETCTN Biorepository			
PRE-PROGRESSION (if applicable, see Section 5.4.2)					
	• 4-8 formalin fixed cores ¹	ETCTN Biorepository			
¹ For new biopsies, a copy of the radiology and operative reports from the tissue removal procedure must					
be sent with the tissue	be sent with the tissue to the ETCTN Biorepository. When completed, upload the corresponding				

pathology reports to Rave.

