5.4 Specimen Collection and Processing

5.4.1 Biopsy Collection Procedure

Mandatory core biopsy specimens will be obtained at two time points. The first ("pretreatment") biopsy will be obtained before beginning study treatment (after informed consent is obtained and up to 14 day prior to cycle 1 day 1). The second ("on-treatment") biopsy will be performed during cycle 2, days 3-5.

A third, optional ("pre-progression") biopsy will be collected from patients who meet certain criteria and provide informed consent for this biopsy (see Section 5.4.2 below).

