5.4.2 Optional "Pre-Progression" Tumor Biopsy

The investigators will seek to evaluate the RAD51, MGMT, and SLFN11 assays in patients who have evidence of clinical benefit from the study drug but later show evidence of radiographic progression not meeting RECIST criteria for progressive disease.

To undergo this biopsy, all of the following criteria must be met:

- 1. The patient has provided informed consent for the optional tumor biopsy, which is part of the informed consent document for this study.
- 2. The patient has evidence of clinical benefit from study treatment manifest by either:
 - a. RECIST complete or partial response within the first 6 months of study treatment
 - b. Stable disease, by RECIST criteria, of at least 4 cycles (12 weeks) duration
- 3. At a subsequent timepoint, the patient has study-specified imaging showing evidence of radiographic disease progression, but which does not meet RECIST criteria for progressive disease (RECIST + 5-19% from the baseline study) and the patient lacks clinical progression, and the investigator intends to continue the study treatment.

When all of these criteria apply, a third ("pre-progression") tumor biopsy will be performed. The same procedures as described in Section 5.4.1 will apply to this biopsy. The biopsy will occur during days 3-5 of the next treatment cycle initiated following the timepoint at which these criteria are met, 2-6 hours post AM olaparib and temozolomide treatment. The same site of disease should be biopsied if at all possible.

If questions arise regarding whether a given patient is considered appropriate for the optional biopsy, the treating investigator should discuss with the principal investigator prior to the procedure.

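### For MGMT and SLFN11, change at progression compares a drug-free biopsy with a post-dose one, so on-drug effect and acquired change cannot be separated

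*Combined protocol and SAP*

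**What the plan says.** Objective 1.3.3 uses an optional third biopsy, in patients who first benefit and then show early progression, to "evaluate for changes in the status of the RAD51 foci, MGMT, and SLFN11 assays at that time".

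Three biopsies are described:

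- **Pre-treatment.** Section 5.4.1 says it "will be obtained before beginning study treatment"; Section 5.1 sets the window as "after informed consent and within 14 days of Cycle 1 Day 1".
- **On-treatment.** Mandatory, at cycle 2 days 3-5, 2-6 hours after the morning dose of both drugs (Sections 5.1 and 5.4.1). The yield is "4-6 formalin fixed cores".
- **Pre-progression.** Optional. Section 5.4.2 says: "The biopsy will occur during days 3-5 of the next treatment cycle initiated following the timepoint at which these criteria are met", again 2-6 hours after the morning dose of both drugs, and from the same disease site if possible.

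RAD51 is read on all three (Sections 5.6 and 5.7.2.2). MGMT and SLFN11 are read on the first and third only. Section 5.8.1.2 states this for MGMT: "MGMT protein (and possibly RNA expression) will be evaluated using established methodology in pre-treatment and optional 'pre-progression' biopsies". Section 5.8.2.2 and the Section 5.6 table do the same for SLFN11.

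The background takes a different line for MGMT. Section 2.5.2.1 cites re-expression as a route to temozolomide resistance and concludes that "reevaluating the status of MGMT protein expression in the on-treatment and preprogression biopsies is also of interest". Section 2.5.2.2, on SLFN11, has no such sentence.

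Section 9.4.1.4 relates both markers to ORR and PFS. It defines no analysis of change over time.

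**The concern.** The two samples compared for MGMT and SLFN11 differ in two ways at once: time on therapy, and whether the tumor was sampled hours after dosing. Any difference found is the sum of the two. A shift caused by recent dosing could be reported as acquired change, or a real change could be hidden by a shift the other way.

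The question matters for MGMT because Section 2.5.2.1 describes it as the enzyme that removes the lesion temozolomide makes, and gives resistance as the reason for testing it again. At stake is the interpretation of objective 1.3.3 for two of its three assays.

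**Working it through.** The plan states no figure on this point, so there is none to reproduce. The check is whether the planned samples can identify the quantity of interest.

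**1. Sample and assay grid** (Sections 5.1, 5.4.1, 5.4.2, 5.6, 5.7.2, 5.8.1, 5.8.2)

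| Biopsy | Study drug at sampling | RAD51 | MGMT | SLFN11 |
|---|---|---|---|---|
| Pre-treatment | none | yes | yes | yes |
| Cycle 2 days 3-5 | 2-6 h after dose | yes | no | no |
| Pre-progression, days 3-5 | 2-6 h after dose | yes | yes | yes |

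RAD51 has one pair matched on cycle day and hours after dose. MGMT and SLFN11 have none.

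**2. What each contrast estimates.** Let b be the baseline level, a the on-drug effect at this sampling time, c2 the change acquired by cycle 2, and cP the change acquired by the pre-progression biopsy.

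- Pre-treatment = b
- Cycle 2 = b + a + c2
- Pre-progression = b + a + cP

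As planned, the only contrast is pre-progression minus pre-treatment = a + cP. With rows (1,0,0) and (1,1,1) for (b, a, cP), the design has rank 2 for 3 unknowns. More patients do not help.

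Adding cycle 2 gives pre-progression minus cycle 2 = cP - c2, in which a cancels. If c2 = 0, the added row is (1,1,0), the rank is 3, and cP is estimable. If c2 is not zero, this contrast captures only change after cycle 2, and cycle 2 minus pre-treatment = a + c2 is still a mixture. The extra time point therefore removes a from one comparison but does not isolate every component. The cancellation also assumes that a is the same at both visits.

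**3. Illustration of size** (assumed; the documents give no acute effect for either marker)

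- If dosing lowers measured MGMT by 30-60%, a true 1.5-fold rise reads as 1.5 × 0.7 = 1.05 down to 1.5 × 0.4 = 0.6.
- Under the same fall, a true 2-fold rise reads as 2 × 0.7 = 1.4 down to 2 × 0.4 = 0.8.
- If dosing raises it by 30-60%, no true change reads as a 1.3- to 1.6-fold rise.
- If dosing has no effect, the planned contrast is unbiased.

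**4. Tissue** (Sections 5.1 and 5.6). The on-treatment biopsy has 10 slides assigned, all for RAD51. Adding 10 for MGMT and 10 for SLFN11 makes 30. The pre-progression biopsy already carries 10 + 10 + 10 = 30 slides from 4-8 cores, and the pre-treatment biopsy carries 30 slides plus 2 cores for sequencing, also from 4-8. The minimum of 4 cores is common to all three.

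**The case against.** The strongest reply has four parts.

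- **The objective is modest.** It is exploratory, rests on an optional biopsy in a subset of 22 patients, and asks only about change in status. A before/after status can be reported without attributing it to a cause, and Section 9.4.1.4 plans no test of change. This stands: a reader might infer that objective 1.3.3 cannot be answered at all, but the text does not support that.
- **No acute effect is shown.** Nothing in the documents says that either drug shifts measured MGMT or SLFN11 within hours or days. Section 2.5.2.1 describes MGMT expression as epigenetically silenced in some tumors. This stands too: a reader might infer that the comparison is biased, but the documents show only that bias cannot be excluded. SLFN11 has no supporting sentence like the one for MGMT.
- **The on-treatment sample is not a clean reference.** It follows a full cycle, so its difference from baseline is not a pure acute effect, and change already present by cycle 2 drops out of the later contrast. Under Sections 7.2 and 7.3, doses may have been reduced or one agent stopped before the pre-progression biopsy, and the lesion may differ. A reader might infer that RAD51 is free of the problem. It has a timing-matched pair, but the same limits apply. This shapes how results should be reported; it does not restore the two-point comparison.
- **Tissue may be short.** The on-treatment upper limit is 6 cores rather than 8, MGMT and SLFN11 rank lowest in Section 5.6, and Section 5.7.1.3 reports sequencing for 16 of 22 patients (73%) because of access and tumor content problems. That is consistent with a deliberately smaller assay set, although no section says so. It supports limiting the request to tissue left after RAD51.

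**Conclusion.** The point holds as a limit on interpretation. For MGMT and SLFN11, on-drug effect and acquired change are fully aliased in the only comparison planned. For MGMT there is also an inconsistency: Section 2.5.2.1 names the on-treatment biopsy, while Sections 5.6 and 5.8.1 leave it out. The background sentence expresses interest rather than a commitment, but the two should agree. For SLFN11 the case is the aliasing alone.

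The size of any error is unknown, because it depends on an acute effect that the documents neither report nor exclude. The conclusion itself rests only on the sampling times and the assay grid. The scope is one exploratory objective. This is an inexpensive improvement, not a threat to the trial's conclusions.

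**What to change.** - **Time point.** In Sections 5.6 and 5.8.1, and in 5.8.2 where tissue allows, add the existing cycle 2 day 3-5 biopsy for patients who also have a pre-progression biopsy. Use only tissue left after RAD51. This also reconciles Section 2.5.2.1 with the biomarker plan.
- **Reporting.** In Section 9.4.1.4, state that all three time points are reported descriptively. Give pre-progression versus cycle 2 as the comparison matched on cycle day and hours after dose, alongside pre-progression versus pre-treatment. Call cycle 2 versus pre-treatment early on-treatment change, not acute drug effect. Note that dose level and lesion may differ between samples.
- **Fallback.** Where on-treatment tissue is not available, state that the baseline contrast does not separate drug effect from acquired change.

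**Cost.** Up to 20 more unstained slides per such patient, plus staining and reading, with no new biopsy. Section 5.8 has MGMT and SLFN11 slides cut in batch after study completion, which favors the change. The current version already reports sequencing results, however, and the documents do not say how much on-treatment tissue remains. Incomplete yield should be expected.

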5.8.2 SLFN11 Expression

5.8.2.1 Specimen Receipt and Processing at the ETCTN Biorepository

For this correlative, 10 unstained, uncharged slides from the pre-treatment and pre-progression biopsy (if applicable) will be created, labeled appropriately, and sent to the laboratory of [name] of the National Cancer Institute for SLFN11 expression analysis. The slides will be packed at ambient conditions and sent by overnight courier to:

Translational Pharmacodynamics Research Group Developmental Therapeutics Branch, CCR, NCI, NIH [name][name] 20892 [contact]

Prior to shipment, an e-mail will be sent to: [name] ([contact]) and [name] ([contact]) to inform the laboratory of the shipment.

5.8.2.2 Site Performing Correlative Study

SLFN11 protein (and RNA expression) will be evaluated using established methodology in pretreatment and optional 'pre-progression' biopsies by immunohistochemistry and mRNA in the laboratory of [name], Developmental Therapeutics Branch, NCI.

6. TREATMENT PLAN

6.1 Agent Administration

Treatment will be administered on an outpatient basis. Reported adverse events and potential risks are described in Section 10. Appropriate dose modifications are described in Section 7. No investigational or commercial agents or therapies other than those described below may be administered with the intent to treat the patient's malignancy.

	Reg	gimen Descr	iption		
Agent	Premedications; Precautions	Dose	Route	Schedule	Cycle Length
Olaparib	Do not consume grapefruit juice	200 mg	Tablets PO BID	Days 1-7	21 dava
Temozolomide (TMZ)	Ondansetron 8 mg PO once with TMZ.	75 mg/m ²	Capsules PO once daily	Days 1-7	- 21 days (3 weeks)
	Take on an empty stomach				

TMZ=temozolomide; PO=oral administration, BID=twice per day.

The patient will be requested to maintain a medication diary of each dose of medication. The medication diary will be returned to clinic staff at the end of each course.

6.1.1 Olaparib

Patients will be administered olaparib twice daily (BID). Olaparib tablets should be taken at the same time each day, approximately 12 hours apart with one glass of water. The first olaparib dose of the day should be taken concomitantly with TMZ. The olaparib tablets should be swallowed whole and not chewed, crushed, dissolved or divided. Olaparib tablets can be taken with or without food; however, since the morning dose is taken with TMZ, both agents will be taken together on an empty stomach for the morning dose. It is prohibited to consume grapefruit, grapefruit juice, or Seville oranges while on olaparib therapy.

If vomiting occurs shortly after the olaparib tablets are swallowed, the dose should only be replaced if all of the intact tablets can be seen and counted. Should any patient enrolled on the study miss a scheduled dose of olaparib for whatever reason (*e.g.*, as a result of forgetting to take the tablets or vomiting), the patient will be allowed to take the scheduled dose of olaparib up to a maximum of 2 hours after that scheduled dose time. If greater than 2 hours after the scheduled dose time, the missed dose of olaparib is not to be taken and the patient should take their allotted dose at the next scheduled time.

6.1.2 Temozolomide

Patients will be administered TMZ once daily (QD). The TMZ capsules should be swallowed whole with a glass of water and not opened or chewed. To reduce nausea, TMZ should be taken

on an empty stomach and patients will take ondansetron 8 mg PO once concurrently with the TMZ dose during cycle 1. If patients have a medical contraindication to ondansetron, another anti-emetic may be substituted. The use of ondansetron beyond cycle 1 is at the discretion of the principle investigator.

TMZ is rapidly and completely absorbed after oral administration with a peak plasma concentration achieved in a median of 1 hour. Food reduces the extent of TMZ absorption.

If vomiting occurs shortly after the temozolomide tablets are swallowed, the dose should only be replaced if all of the intact tablets can be seen and counted. Should any patient enrolled on the study miss a scheduled dose of temozolomide for whatever reason (*e.g.*, as a result of forgetting to take the tablets or vomiting), the patient will be allowed to take the scheduled dose of temozolomide up to a maximum of 12 hours after that scheduled dose time. If greater than 12 hours after the scheduled dose time, the missed dose of temozolomide is not to be taken and the patient should take their allotted dose at the next scheduled time.

6.2 General Concomitant Medication and Supportive Care Guidelines

Because there is a potential for interaction of olaparib with other concomitantly administered drugs, the case report form must capture the concurrent use of all other drugs, over-the-counter medications, vitamins, nutritional supplements, or alternative therapies at the time of enrollment and throughout the study. The case report form should capture the dates of administration (including start/end dates if known), dosage (including dosing frequency/schedule), and reason for use. The Principal Investigator should be alerted if the patient is taking any agent known to affect or with the potential for drug interactions. The study team should check a frequently-updated medical reference for a list of drugs to avoid or minimize use of. Appendix B (Patient Drug Information Handout and Wallet Card) should be provided to patients if available.

6.2.1 Dietary Restrictions and Over-the-Counter/Self-Medication

It is prohibited to consume grapefruit, grapefruit juice, Seville oranges, or Seville orange juice while on olaparib therapy. The use of any natural/herbal products or other traditional remedies should be discouraged.

6.2.2 Medications that May NOT be Administered

No other anti-cancer therapy (chemotherapy, immunotherapy, hormonal therapy [hormone replacement therapy is acceptable], radiotherapy, biological therapy, or other novel agent) is to be permitted while the patient is receiving study medication.

Live virus and live bacterial vaccines should not be administered while the patient is receiving study medication and during the 30-day follow-up period. An increased risk of infection by the administration of live virus and bacterial vaccines has been observed with conventional chemotherapy drugs and the effects with olaparib are unknown.

6.2.3 Restricted Concomitant Medications

6.2.3.1 Strong or Moderate CYP3A Inhibitors

Known strong CYP3A inhibitors (*e.g.*, itraconazole, telithromycin, clarithromycin, boosted protease inhibitors, indinavir, saquinavir, nelfinavir, boceprevir, telaprevir) or moderate CYP3A inhibitors (ciprofloxacin, erythromycin, diltiazem, fluconazole, verapamil) should not be taken with olaparib.

6.2.3.2 Strong or Moderate CYP3A Inducers

Strong (*e.g.*, phenobarbital, phenytoin, rifampicin, rifabutin, rifapentine, carbamazepine, nevirapine, enzalutamide and St John's Wort) and moderate CYP3A inducers (*e.g.*, bosentan, efavirenz, modafinil) of CYP3A should not be taken with olaparib.

